4.2.6 Ophthalmic Measurements

Participants have a standard of care ocular evaluation in accordance with the SoA (Sections 1.3-1.4 of the protocol).

Document: S:\Q_146\Q_03974\MEK-NF-201\Prog_Stat\Documentation\SAP\MEK-NF-201 SAP v1.0.0.docx

4.3 Other Measures

4.3.1 Participant Disposition

Participant disposition data is primarily collected on the 'End of Study' case report form (CRF) page when a participant completed or discontinued from the study. The following data will be summarized:

- Participants in each analysis set (I.e. Full Analysis Set, Safety Analysis Set, Per-Protocol Set)
- Participants who complete the Treatment Phase
- Participants who discontinued from study in the Treatment Phase and reason for discontinuation
- Participants who discontinued from treatment in the Treatment Phase and reason for discontinuation
- Participants withdrawing consent and reason for withdrawal
- Participants who complete Treatment Phase and do not enter LTFU Phase and reason for not entering LTFU Phase
- Participants entering the LTFU Phase
- Participants who discontinued from study in the LTFU Phase and reason for discontinuation
- Participants who discontinued from treatment in the LTFU Phase and reason for discontinuation
- Participants withdrawing consent in the LTFU Phase and reason for withdrawal

4.3.2 Protocol Deviations

Protocol deviations are reviewed in accordance with the Protocol Deviation Plan. All deviations will be reviewed prior to database lock to determine which deviations are deemed important to report in the CSR in accordance with ICH E3 guidelines. A CSR reportable protocol deviation is typically considered a significant deviation that should be addressed in the CSR as it may impact the accuracy, interpretation, and/or reliability of the study data, participant rights, safety, or well-being. Major protocol deviations are defined as reportable deviations that may impact the accuracy and or reliability of the efficacy data. As described in Section 3.2, any participants with major reportable protocol deviation leads to exclusion from the PPS.

4.3.3 Demographics

Demographic data are primarily collected on the 'Demographics' CRF page at screening. The following data will be summarized:

- Age at time of consent (years)
- Sex
- Childbearing potential at screening
- Ethnicity
- Race
- Kamofsky/Lanksy Performance Status at baseline (Cycle 1 Day 1)

Missing demography data will be handled according to the rules specified in Section 5.5.2.2.

Document: S:\Q_146\Q_03974\MEK-NF-201\Prog_Stat\Documentation\SAP\MEK-NF-201 SAP v1.0.0.docx

Author:

SpringWorks Therapeutics Protocol Number: MEK-NF-201

4.3.4 Baseline Participant Characteristics

Baseline participant characteristics include characteristics that participants presented with prior to the first administration of study treatment.

4.3.4.1 Baseline Disease Characteristics

Tumor history and location is recorded at screening on the "Plexiform Neurofibroma History" CRF. History of tumor therapies, such as surgery and radiotherapy, and baseline tumor volume will also be assessed. The full list of disease characteristics and history to be presented in summaries is as follows:

- Target tumor location
- Target tumor type (nodular, solitary nodular, typical) by central reader (reader A)
- Time since diagnosis (in months)
- NF1 mutation status (CLIA/COA testing)
- Target tumor progression at baseline
- Reported morbidities
- · Prior PN treatments
- Prior PN surgery
- Prior PN radiotherapy

Prior PN treatment information will be taken from the 'Prior Plexiform Neurofibroma Surgeries', 'Prior Plexiform Neurofibroma Radiotherapy' and 'Prior Plexiform Neurofibroma Targeted Therapies/ Medication' CRF pages.

4.3.5 Medical History

Medical history contains information about conditions that a participant might have suffered from prior to the first administration of study treatment or conditions that were ongoing at the time of the first administration of study treatment.

Medical history includes any history of clinically significant disease. Cancer history will include cancer type, date of diagnosis, and an assessment of prior surgery, prior radiotherapy, prior drug therapy including start and stop dates, best response and reason for discontinuation.

4.3.5.1 Coding of Medical History Terms

The medical history term (Investigator term) is assigned to the LLT, and a PT will be classified by a HLT, a HLGT and a SOC according to the MedDRA thesaurus, Version 24.0 or higher, depending on the latest version available during the study.

Although there can be multiple SOCs for a PT, each PT will be linked with one SOC, namely the primary SOC which is automatically assigned by MedDRA via one HLT, HLGT route.

The following coding data will be presented:

- LLT
- PT
- Coding data per primary SOC:
 - HLT
 - HLGT

Document: S:\Q_146\Q_03974\MEK-NF-201\Prog_Stat\Documentation\SAP\MEK-NF-201 SAP v1.0.0.docx

Author:

Medical history will be reported on a per-participant basis. This means that even if a participant suffered the same clinical event repeatedly (i.e., events mapped to the same PT), the event will be counted only once and the earliest date will be regarded as start date of the event and the latest date will be regarded as stop date of the event.

The same rule for counting applies for PTs mapped to the same HLT and for HLTs mapped to the same HLGT and for HLGTs mapped to the same SOC.

4.3.6 Concomitant Medications and Procedures

Concomitant medications and procedures are defined as any medication or procedure that did not end prior to first dose of study treatment or did not start after the applicable safety follow-up period.

Medication and procedures will be considered prior if they stopped before the first dose of study treatment. Concomitant medications data is collected throughout the study on the 'Concomitant Medications' CRF page, Concomitant procedures data is collected throughout the study on the 'Concomitant Procedures' CRF page.

Missing concomitant medications dates will be handled according to the rules specified in Section 5.5.2.4.

4.3.6.1 Coding of Concomitant Medication Terms

Concomitant medications are classified according to active drug substance using the World Health Organization-Drug Dictionary (WHO-DD), Global B3 Version Mar 2021.

In this study, anatomical therapeutic chemical (ATC) codes are defined to the 4th level.

Although there can be multiple ATC classes for a drug, each drug will be linked with one ATC class which will be assigned manually during the coding process, based on information about the indication and route in relation to the study therapeutic area. This one ATC class will be indicated as the 'primary' ATC class, and only the primary class will be presented.

4.3.7 Exposure to Study Treatment

There is only a single dose level on this study. All participants receive mirdametinib at a dosage level of approximately 2 mg/m² BID (up to a maximum of 4 mg BID). All participants follow an intermittent dosing schedule of 3 weeks on/1 week off, which creates 28-day cycles. The Treatment Phase comprises 24 cycles.

Participants enrolled in the LTFU Phase of the study continue taking the last dose assigned in the Treatment Phase (approximately 2 mg/m² BID [maximum dose of 4 mg BID]) of mirdametinib, unless a dose modification is required (e.g., body surface area [BSA] change), on an intermittent (3 weeks on/1 week off) dosing schedule in 28-day cycles. This phase is of indefinite length.

At any point in the study, if a participant exhibits sufficiently worrisome AEs of significant toxicity, dosing can be interrupted and/or reduced. If dose is reduced, then it may only be increased in the Treatment Phase following a BSA change and with approval from the medical monitor and sponsor. The criteria for dose reduction, and the reduced dose plan are in Section 6.6 of the protocol.

The following exposure-related measures will be summarized:

Document: S:\Q_146\Q_03974\MEK-NF-201\Prog_Stat\Documentation\SAP\MEK-NF-201 SAP v1.0.0.docx Author:

SpringWorks Therapeutics Protocol Number: MEK-NF-201

- Duration of exposure (months)
- Total duration of exposure (participant years)
- Time to first dose reduction (months)
- Participants with dose modification along with reasons for dose modification
- Participants with dose reduction along with reasons for dose reduction
- Participants with dose interruption along with reasons for dose interruption
- · Actual dose intensity
- Relative dose intensity

Duration of exposure in months is calculated as (Date of last dose - Date of first dose +1)/30.4375.

Total duration of exposure in participant years is calculated as (total sum of all participants duration of exposure in months)/12

Time to first dose reduction in months is calculated as (Date of first dose reduction - Date of first dose + 1)/30.4375

Actual and relative dose intensity will be calculated as follows:

- Actual dose intensity cumulative dose received/number of prescribed dosing days.
- Relative dose intensity 100*(cumulative dose received/planned dose).

Cumulative dose received will be calculated using dispensed and returned pill counts. Actual dose intensity will also be derived accounting for BSA.

4.3.8 Pharmacokinetic and Pharmacodynamic Analyses

A separate supplementary SAP will describe the PK parameters, PopPK/PD models, and analyses. Plasma PK collection dates, times, and concentration results will be displayed in a data listing.

Statistical Methodology

5.1 General Statistical Methods

5.1.1 General Information

All analysis data sets, and output will be produced by the Biostatistics Department of Quanticate Ltd using the SAS® system Version 9.4 or higher.

5.1.2 Default Descriptive Statistics and Data Rules

Unless otherwise stated, summary statistics including the number of participants, mean, standard deviation (SD), median, minimum, and maximum, will be presented by age cohort for all continuous variables. Minimum and maximum values will be presented to the same decimal

Document: S:\Q_146\Q_03974\MEK-NF-201\Prog_Stat\Documentation\SAP\MEK-NF-201 SAP v1.0.0.docx

Author:

Protocol Number: MEK-NF-201

precision as the raw values, the mean and median values to one more, and the standard deviation, to two more decimal places than the raw values.

For categorical variables, per category, the absolute counts (n) and percentages (%) of participants in each with data, and if appropriate, the number of participants with missing data, will be presented for each age cohort. All percentages will be presented to one decimal place.

For AEs reported on a per-participant basis, medical history and concomitant medications, the denominator for the percentage calculation will be the number of participants in each age cohort. A participant will be considered at risk if the participant is in the Safety Analysis Set/FAS and entered the respective study period.

5.2 Hypotheses and Decision Rules

The primary efficacy endpoint will be assessed separately for each age cohort. The lower limit of the 95% confidence interval for the primary endpoint will be compared to a minimal clinically relevant response in the age groups.

The study was originally set up using minimally clinically relevant thresholds of 23% in adult participants and 42% in pediatric participants. As such, the null hypothesis for the participants ≥ 18 years of age at baseline (the adult population) is that the ORR is equal to 23%. The alternative hypothesis is that the ORR is not equal to 23%. The null hypothesis for participants 2 to 17 years of age at baseline (the pediatric population) is that the ORR is equal to 42%. The alternative hypothesis is that the ORR is not equal to 42%.

Due to emerging data and discussion with the FDA, as outlined in Section 7 (changes to Planned Analyses), the threshold for the pediatric cohort was updated. The null hypothesis for participants 2 to 17 years of age at baseline (the pediatric population) is that the ORR is equal to 20%. The alternative hypothesis is that the ORR is not equal to 20%.

5.3 Covariates

No covariates will be considered for the primary efficacy analysis. For all mixed models for repeated measures (MMRM) used in secondary and exploratory analyses, the only covariate included will be the respective baseline score.

5.4 Multi-Center Data

This is a multi-center study and all the data from all sites will be pooled. No consideration of center effect is planned for the listed analyses.

5.5 Handling of Missing Data

Missing data will only be imputed in the following cases:

Document: S:\Q_146\Q_03974\MEK-NF-201\Prog_Stat\Documentation\SAP\MEK-NF-201 SAP v1.0.0.docx

5.5.1 Secondary Efficacy Endpoints

5.5.1.1 Change from Baseline in QoL assessed by the age specific PedsQL

If ≤ 50% of questions in a given scale are missing, then the scale score will be imputed as the mean of the non-missing questions. If > 50% of questions are missing, then the scale score should not be calculated for that scale. The main analysis for this endpoint will be a mixed model for repeated measures (MMRM), which treats all missing data as missing at random (MAR).

A sensitivity analysis will be performed to assess the potential impact of this assumption if some data is missing not at random (MNAR). For this purpose, monotone and non-monotone missing values will be treated differently. Non-monotone missing values are values missing intermittently, where a participant may miss some PRO assessments but has PRO assessments for the same score later in the study. Monotone missing values are such that once a value is missing for a given score, no subsequent values for this score are available. Any given participant may have a combination of non-monotone and monotone missing values.

Non-monotone missing values are assumed to be MAR so will not be directly imputed as the analysis by MMRM already makes this assumption. Monotone data, however, will be considered MNAR and imputed to be equal to the participant's baseline score. This choice of imputation represents a negative outcome of no improvement in QoL for each participant.

The details of the sensitivity analysis to be performed with this imputed data are given in Section 6.11.2.2.

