4.1.2.2.1 Pediatric Quality of Life Inventory (PedsQL)

The PedsQL 4.0 Generic Core Scales are multidimensional self-report and parent proxy-report scales to assess health-related quality of life (HRQoL) in children, adolescents, young adults, and adults with a recall period of 7 days. It is a brief standardized HRQoL scale with good reliability and validity. It consists of a 23-item core measure of global QoL and can be completed in approximately 5 minutes. The questions are split into four dimensions, each of which can have an overall scale score calculated.

The secondary endpoint Change from baseline in quality of life (QoL) assessed by the age specific Pediatric Quality of Life Inventory will be evaluated using the following PedsQL scores:

- Physical functioning,
- Emotional functioning,

Document: S:\Q 146\Q 03974\MEK-NF-201\Prog Stat\Documentation\SAP\MEK-NF-201 SAP v1.0.0.docx

Author:

- Social functioning,
- School/work functioning,
- Total score.

PedsQL items are answered on a Likert scale with responses ranging from 0 to 4 (where 0 means it is never a problem and 4 means it is almost always a problem). These items are then reverse scored and linearly transformed to a 0-100 scale as follows: 0=100, 1=75, 2=50, 3=25, 4=0. Overall scale scores are calculated as the mean of the scores for the questions in said scale (or of all questions for the total score).

Participants complete PedsQL at the time points specified in the SoA (Sections 1.3-1.4 of the protocol).

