5.5.1.2 Change from Baseline using the NRS-11

If ≥4 of the 7 NRS-11 readings associated with a single visit are missing, then the score for that visit will be treated as missing. If <4 readings are missing, the value associated with a visit will be the average of the non-missing readings.

A sensitivity analysis, similar to that described for PedsQL in Section 5.5.1.1, will be performed to assess the impact of MNAR data on the NRS-11 results. The imputation described in Section 5.5.1.1 will be performed for missing NRS-11 data, and the sensitivity analysis will be performed as detailed in Section 6.11.2.3.

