5.5.1.3 Change from Baseline using the PII

If >3 of the 6 PII questions associated with a single assessment are missing, then the score for that assessment will be treated as missing. Otherwise, the score for a given assessment will be taken as the average of the non-missing assessment scores. If ≥4 of the 7 PII assessments corresponding to a single visit are missing, then the score for that visit will be treated as missing. Otherwise, the value associated with a visit will be the average of the non-missing readings.

A similar sensitivity analysis will also be performed to assess the impact of MNAR data on the PII results. The imputation described in Section 5.5.1.1 will be performed for missing PII data, and the sensitivity analysis will be performed as detailed in Section 6.11.2.3.

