An MMRM will be fitted separately by age cohort and questionnaire type for each PedsQL score listed in Section 4.1.2.2.1. Change from baseline in PedsQL score will be the dependent variable, visit will be fitted as a fixed effect, and baseline PedsQL score used as a covariate. Covariance structures will be trialed in the order of decreasing complexity, with the first structure that converges without error used. The structures tested are as follows: Unstructured, Heterogenous Toeplitz, Heterogenous Autoregressive, Autoregressive, Heterogenous Compound Symmetry, Compound Symmetry, Variance Components. A Kenward-Roger approximation will be used for the degrees of freedom. This model will be fitted twice, once using only data through Cycle 13, and once including data from the entire study (timepoints with < 5 subjects will not be presented). EOT and unscheduled visits will be mapped to the closest scheduled tumor visit following the rules outlined in Table 13, and will only be included in the model if the participant has no other record at that timepoint. For the MMRM change from baseline tables, the least square (LS) Means estimates will be presented with associated standard errors, 95% Cls and p-values by visit. Plots of the LS Means estimates over time with associated 95% Cl bands will be presented separately by age cohort and questionnaire type for both models.

Box and whiskers plots of change from baseline in total score will be presented by visit and confirmed objective response status for the adult cohort, pediatric cohort self-report, and pediatric cohort parent proxy separately.

A waterfall plot of change from baseline will be presented by visit for adult cohort, pediatric cohort self-report and pediatric cohort parent proxy separately for each PedsQL domain at Cycles 5 and 13 with a line representing the respective within-patient meaningful change threshold derived by anchor-based analysis. This plot will be color-coded by confirmed objective response status.

Additionally, a sensitivity analysis will be performed for each PedsQL score using the imputed data described in Section 5.5.1.1. The MMRM analysis described above will be performed with data up to Cycle 13. LS Means estimates, associated standard errors, 95% Cls and p-values will be presented by visit.

Document: S:\Q_146\Q_03974\MEK-NF-201\Prog_Stat\Documentation\SAP\MEK-NF-201 SAP v1.0.0.docx

Author:

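### Setting every monotone-missing PRO score to baseline is not a negative outcome for a participant who had already worsened, so the only planned MNAR check can come out above the main MMRM

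*SAP*

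**What the plan says.** The main PedsQL analysis is an MMRM on change from baseline that treats missing data as missing at random (MAR). SAP 5.5.1.1 then plans one sensitivity analysis for informative dropout and splits the gaps in two.

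- Intermittent gaps: "Non-monotone missing values are assumed to be MAR so will not be directly imputed".
- Gaps with no later score: "Monotone data, however, will be considered MNAR and imputed to be equal to the participant's baseline score". No exception is made for a participant whose last score was below baseline.

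The justification follows: "This choice of imputation represents a negative outcome of no improvement in QoL for each participant".

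The pain scores take the same rule by reference. SAP 5.5.1.2: "The imputation described in Section 5.5.1.1 will be performed for missing NRS-11 data". SAP 5.5.1.3: "The imputation described in Section 5.5.1.1 will be performed for missing PII data". In SAP 6.11.2 the imputed data go back into the same model: "The MMRM analysis described above will be performed with data up to Cycle 13". LS means, standard errors, confidence intervals and p-values are reported by visit. The SAP describes no other MNAR analysis for these scores.

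**The concern.** Setting the score to baseline sets the change to zero. That is unfavourable for someone who was improving. For someone already worse than baseline it replaces an observed loss with no loss, so the stated property does not hold for each participant.

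The documents make this kind of dropout realistic. Radiographic progression ends the Treatment Phase (SAP 2.2), and SAP 6.10 lists progression, adverse events and being too ill among the reasons for missing PRO data. In a single-arm, open-label trial, PRO results have little other protection against selective loss. If people leave because they are doing badly, a sensitivity result at or above the main one would be read as reassurance when it comes partly from the imputation rule.

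**Working it through.** **Inputs.** The documents supply the rule, the model, the Cycle 13 horizon, about 50 participants per cohort, and the score direction. For PedsQL, "These items are then reverse scored and linearly transformed to a 0-100 scale", so higher is better and worsening is a negative change; for NRS-11 and PII the signs reverse. They give no expected PRO effect, SD, between-visit correlation or dropout rate, so there is no plan figure to reproduce. Every effect size, SD, correlation and dropout rate below is an assumption.

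**Step 1: one participant.** Simplify to two visits with equal variances. Let mu be the mean change among those who stay (the same at both visits), rho the between-visit correlation, and L a leaver's last observed change.

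- Value implied by the main MMRM: mu + rho(L - mu)
- Value under the SAP rule: 0
- The SAP rule is the more favourable when L < -mu(1 - rho)/rho

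Thresholds for L:

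| mu | rho 0.5 | rho 0.7 |
|---|---|---|
| 4 | -4.0 | -1.7 |
| 6 | -6.0 | -2.6 |

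For example, -4 x 0.3/0.7 = -1.7. At mu = 6 and rho = 0.4 the threshold is -6 x 0.6/0.4 = -9.

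**Step 2: the cohort mean.** Let a fraction f leave with mean last change L.

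- Main (MAR): mu + rho x f x (L - mu)
- SAP rule: (1 - f) x mu

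With mu = 6 and f = 0.25, the SAP rule gives 0.75 x 6 = 4.5 whatever L is. The main estimate is:

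| Mean L | rho 0.7 | rho 0.5 | rho 0.4 |
|---|---|---|---|
| -12 | 2.85 | 3.75 | 4.20 |
| -8 | 3.55 | 4.25 | 4.60 |
| -4 | 4.25 | 4.75 | 5.00 |
| 0 | 4.95 | 5.25 | 5.40 |

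In the -8 row the main estimate is 6 - 3.5 rho, which equals 4.5 at rho = 1.5/3.5 = 0.43. Above that correlation the sensitivity result is the better-looking one; below it the rule is conservative. Under random dropout (mean L = 6) the main estimate is 6 and the rule gives 4.5.

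**Step 3: the SAP model.** A small simulation fitted change on visit and baseline with unstructured covariance: N = 50, five visits to Cycle 13, residual SD 12, Cycle 5 to Cycle 13 correlation about 0.59, and 30% leaving after Cycle 5. Each scenario had 40 replicates, so the figures are approximate. Mean Cycle 13 estimates:

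| Who leaves | True change | Main | SAP rule |
|---|---|---|---|
| Worst 30% at Cycle 5 | 0 | 0.6 | 2.9 |
| Worst 30% at Cycle 5 | 3 | 2.5 | 4.5 |
| More likely after worsening | 6 | 5.7 | 5.6 |
| Random 30% | 6 | 6.0 | 4.2 |
| Best 30% at Cycle 5 | 6 | 5.9 | 1.5 |

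The constant zeros also shrink the standard error, from about 1.9 to 1.3 in the first row. There, nominally significant benefit rose from 8% to 62% of replicates.

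**Step 4: the alternative.** Take the worse of baseline and last value, min(0, L) on the PedsQL scale. It is never above the SAP rule. For mu at or above 0 and rho between 0 and 1 it is never above the MMRM-implied value either. Its price shows under random dropout. With L normal, mean 6 and assumed SD 15, the mean of min(0, L) is 6 x 0.345 - 15 x 0.368 = -3.5. The cohort mean is then 4.5 - 0.25 x 3.5 = 3.6, against 6 for the main analysis.

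**The case against.** The strongest reply is that the sentence defines its negative outcome as no improvement, which a zero change is. It does not claim a worst case or a bound. That stands, and is why the sentence needs rewording rather than removal; the difficulty is that it extends the label to each participant.

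A reader might infer that any leaver below baseline is treated more kindly than under the main MMRM. The algebra does not support that. The MMRM pulls a leaver towards the cohort mean, so after mild worsening it can predict a gain, and zero is then the harsher value. A reader might also infer that the check will usually exceed the main result. The direction depends on a correlation that the documents do not give, and it reverses at ordinary values.

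The reach is also limited. Only monotone loss before Cycle 13 counts, scores observed before dropout stay in the model, and the tables of reasons for missing data in SAP 6.10 would help to show informative loss. These points stand, but a table of reasons does not correct an estimate.

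Finally, the worse-of rule counts visit-to-visit noise as deterioration. That also stands, and is why it should sit beside the planned analysis rather than replace it.

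**Conclusion.** The point holds in a conditional form. The only planned MNAR analysis for PedsQL, NRS-11 and PII can move towards benefit when participants leave after clear worsening and visits are well correlated. In the worked case it lies about 0.95 points above the main estimate at rho 0.7 (4.5 - 3.55), 0.25 above at rho 0.5, and 0.1 below at rho 0.4. Those sizes rest on assumed effects, correlation and dropout, and on a two-visit simplification; the five-visit simulation also shows the direction depending on who leaves. Where dropout is random, improvers leave or correlation is low, the analysis is conservative as the SAP intends, so the documents do not support calling it anti-conservative in general. Secondary endpoints are affected; the primary response-rate analysis is not.

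**What to change.** Keep the baseline-imputation analysis. In SAP 5.5.1.1, and by reference in 5.5.1.2 and 5.5.1.3, add a second MNAR analysis using the same MMRM to Cycle 13:

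- Impute monotone-missing scores as the worse of baseline and the last observed post-baseline value: the lower for PedsQL, the higher for NRS-11 and PII.
- Use baseline where there is no post-baseline score.
- State whether a single-day Early Termination reading counts as last observed for NRS-11 and PII. That visit has one assessment rather than seven, so under the rule that four or more missing days void a visit score, a literal reading makes it missing.

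Reword the justification in 5.5.1.1 to say that baseline imputation represents no improvement and is not conservative for participants who had already worsened.

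The cost is one extra set of outputs and about one line of derivation code, with no new data. The added estimate is deliberately pessimistic because it counts noise as worsening, and should be labelled so.
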